24. PROTOCOL ATTACHMENTS

24.1 LABORATORY TESTS

Laboratory Tests Detailed List					
Immunology	Performed by	Malignant Hematological Transformation	Performed by	Serology	Performed by
HLA Typing	Central Lab		Central Lab	Hepatitis B Surface Ag	Central Lab
Complete Blood Count	Performed by		Central Lab	HCV Ab	Central Lab
White Blood Cells	Central Lab		Central Lab	HIV	Central Lab
Red Blood Cells	Central Lab	Automated Differential *	Performed by	EBV	Central Lab
Hemoglobin	Central Lab	Neutrophils	Central Lab	CMV	Central Lab
Hematocrit	Central Lab	Lymphocytes	Central Lab	Rheumatology	Performed by
MCV	Central Lab	Monocytes	Central Lab	ESR	Central Lab
MCH	Central Lab	Eosinophils	Central Lab	CRP	Central Lab
MCHC	Central Lab	Basophils	Central Lab	Drug Levels	Performed by
Platelets	Central Lab	Large Unstained Cells	Central Lab		External Lab
Coagulation	Performed by	Neutrophils Abs	Central Lab	Tuberculosis	Performed by
PT_sec	Central Lab	Lymphocytes Abs	Central Lab	Quantiferon Gold	Central Lab
INR	Central Lab	Monocytes Abs	Central Lab		
APTT_Sec	Central Lab	Eosinophils Abs	Central Lab		
Chemistry	Performed by	Basophils Abs	Central Lab		
Glucose	Central Lab	LUC Abs	Central Lab		
Phosphorus	Central Lab	Hematology	Performed by		
Uric Acid	Central Lab	ESR	Central Lab		
Creatinine Serum	Central Lab	Urinalysis **	Performed by		
BUN	Central Lab	Specific Gravity	Central Lab		
Total Protein	Central Lab	pH	Central Lab		
Albumin	Central Lab	Protein	Central Lab		
SGOT(AST)	Central Lab	Glucose	Central Lab		
SGPT(ALT)	Central Lab	Ketones	Central Lab		
Gamma GT	Central Lab	Bilirubin	Central Lab		
Alkaline Phosphatase	Central Lab	Leucocytes	Central Lab		
Bilirubin Total	Central Lab	Erythrocytes	Central Lab		
Calcium	Central Lab	Nitrites	Central Lab		
Sodium	Central Lab	Urobilinogen	Central Lab		
Potassium	Central Lab				
Chloride	Central Lab				
IGA Quant	Central Lab				
IGG Quant	Central Lab				
IGM Quant	Central Lab				
LDH LTOP	Central Lab				
CPK	Central Lab				

* When Large unstained cells are high or equal to 4.5% than the following microscopic parameters will be tested: atypical lymphocytes (% and abs), bands (% and abs), basophils (% and abs), eosinophils (% and Abs), neutrophils (% and abs.), monocytes (% and abs.), lymphocytes (% and abs.), Metamyelocytes (% and abs.), Myelocytes (% and abs.), NRBC (% and abs.), Promyelocytes (% and abs.).

**When urinalysis positive for Protein, WBC, or RBC, the following microscopic parameters will be tested: Leucocytes, Erythrocytes, Granular-Casts, Hyaline-Casts, Mucus, Crystals, and Bacteria

## VERSION HISTORY

Version	Date	Status/Reason for Changes
1.0	12 October 2022	Initial Draft

## 1.0 LIST OF ABBREVIATIONS

Abbreviation	Definition
AE	Adverse Event
AMD	Age-Related Macular Degeneration
BCVA	Best Corrected Visual Acuity
█	█
CFP	Color Fundus Photography
CI	Confidence Interval
CNV	Choroidal Neovascularization
CRF	Case Report Form
CRP	C-Reactive Protein
CSR	Clinical Study Report
DLT	Dose-Limiting Toxicity
DSMB	Data Safety Monitoring Board
ESR	Erythrocyte Sedimentation Rate
EBV	Epstein–Barr Virus
ECG	Electrocardiogram
ETDRS	Early Treatment Diabetic Retinopathy Study
FA	Fluorescein Angiography
FAF	Fundus Autofluorescence (imaging)
FRI	Functional Reading Independence (FRI) Index
GA	Geographic Atrophy
GMP	Good Manufacturing Practice
HBV	Hepatitis B Virus
HCV	Hepatitis C Virus
hESCs	Human Embryonic Stem Cells
HLA	Human Leukocyte Antigen(s)
IB	Investigator’s Brochure
IFU	Instructions for Use
IOP	Intraocular Pressure
LDH	Lactic Dehydrogenase
█	█
MedDRA	Medical Dictionary for Regulatory Affairs
MTD	Maximally Tolerated Dose

Abbreviation	Definition
NEI VFQ-25	National Eye Institute Visual Function Questionnaire-25
██████	████████████████████
PP	Per Protocol
QoL	Quality of Life
RPE	Retinal Pigment Epithelium
SAE	Serious Adverse Event
SD	Standard Deviation
SD-OCT	Spectral Domain Optical Coherence Tomography
SLE	Slit Lamp Examination
████	████████████████████
TEAE	Treatment-Emergent AEs
TE SAE	Treatment-Emergent SAE

## 2.0 INTRODUCTION

### General Overview

CCN\_CT02 is a Phase I/IIa, multicenter, multinational open-label, interventional clinical trial of OpRegen®, a cell-based product composed of retinal pigment epithelium ([RPE](#)) cells, derived from human embryonic stem cells ([hESCs](#)) through a process of directed differentiation, which are implanted as a single administration to the worst vision eye of patients with advanced dry-form age-related macular degeneration ([AMD](#)) and geographic atrophy ([GA](#)) as a cell suspension ([www.ClinicalTrials.gov](http://www.ClinicalTrials.gov) Identifier: NCT02286089). The study involves dose escalation cohorts of targeted suspensions of  $50 \times 10^3$  to  $200 \times 10^3$  cells [REDACTED]

[REDACTED]  Two methods of subretinal surgical administration of OpRegen were employed during the study; 1) pars planar vitrectomy (PPV) and retinotomy or, 2) [REDACTED], which utilized a sclerotomy and [REDACTED] route to access the subretinal space.

### Purpose of the Statistical Analysis Plan (SAP)

The purpose of this document is to provide a description of the statistical methods and procedures to be implemented for the analysis of data from the OpRegen clinical trial CCN-CT02. This document is based on protocol version amendment number 14, dated 9 April 2019. Any revisions to the SAP (both alternative and additional methods) will be made prior to database lock(s) and reasons for such revisions will be described in the final Clinical Study Reports ([CSR](#)).

## 3.0 STUDY OBJECTIVES AND ENDPOINTS

### 3.1 Study Objectives

#### 3.1.1 Primary Objectives

To evaluate the safety and tolerability of human embryonic stem cell-derived retinal pigment epithelium cells (OpRegen), transplanted subretinally to subjects with advanced dry age-related macular degeneration ([AMD](#)) with geographic atrophy ([GA](#)).

#### 3.1.2 Secondary Objectives

To evaluate the preliminary efficacy of OpRegen treatment by assessing the changes in ophthalmological parameters as measured by various methods of primary clinical relevance.

[REDACTED]

---

 Refer to Section 2.3 in the [Investigator Brochure](#) for more information about the Product Description

### 3.2 Study Endpoints

#### 3.2.1 Safety and Tolerability Endpoints

Safety and tolerability of OpRegen treatment will be assessed by:

- Incidence and frequency of treatment emergent adverse events ([AEs](#))
- Treatment emergent changes in the following variable:
  - Ophthalmological evaluation:
    - ✓ Intraocular Pressure ([IOP](#))

[REDACTED]

#### 3.2.4 Efficacy Endpoints of Clinical Relevance

Preliminary efficacy assessments will utilize the below listed parameters:

- Directional change in the geographic atrophy ([GA](#)) lesion area over time
- Overall change in the [GA](#) lesion area of the study eye over time using [SD-OCT](#) and [FAF](#)
- Change from baseline over time in [BCVA](#) as measured by Early Treatment Diabetic Retinopathy Study ([ETDRS](#)) chart
- Change from initial assessment over time in retinal sensitivity (as assessed by microperimetry)
- Change from baseline over time in Reading Speed Test
- Change from baseline over time in Low Luminance [BCVA](#)
- Correlation assessment between quantitative metrics derived from [FAF](#), [SD-OCT](#) and [CFP](#) images
- Correlation assessment between functional and structural changes
- Change over time in National Eye Institute Visual Function Questionnaire-25 ([NEI VFQ-25](#)) Quality of Life ([QoL](#)) score
- Change over time in Functional Reading Independence ([FRI](#)) Index score

### 3.3 Study Hypothesis

As this is an open label, phase I/IIa dose escalation, safety, tolerability, and preliminary efficacy study, neither power assessment, nor formal hypotheses testing were planned for study outcome measures. However, for purposes of data analyses and this SAP, the Sponsor hypothesizes that implantation of OpRegen to subjects with advanced dry-form AMD with GA is safe, well-tolerated and provides evidence of preliminary efficacy based on pre-specified functional and structural assessments.

The primary hypothesis is that there will be no dose-limiting toxicity (DLT) and that implantation of OpRegen to subjects with progressive dry-form AMD with GA will be safe and well-tolerated. For this study DLT is defined as an SAE determined to be product related.

A secondary null hypothesis is that there will be no difference in disease progression, as measured by retinal function and structure, between the treated and untreated regions in the treated eye and between the treated and untreated eye of a subject.

### 3.4 Study Assessments Schedules

Study assessments are described in detail in the protocol and summarized below in [Table 1](#).

**Table 1. Study Assessments**

Assessment	Time points	Primary Endpoints/ Safety	Efficacy Endpoints of Clinical Relevance
Best-Corrected Visual Acuity (BCVA)-ETDRS Retro illuminated 4-meter ETDRS Chart “R” for refraction followed by Chart “1” and “2” BCVA is reported in number of letters read correctly. First, the right eye is tested with Chart 1 and then the left eye is tested with Chart 2. Must be conducted by trained examiner (technician acceptable) and as per “BCVA Instructions Manual”.	[REDACTED]	√	√
Low Luminance Best Corrected Visual Acuity LL BCVA is measured by placing a 2.0-log-unit neutral density filter over the trial frame in front of the study eye and having the participant read the normally illuminated ETDRS chart using a different version of the chart. This test is optional as subjects with low vision will not be able to perform this test and is not applicable for Cohorts 1-3.	[REDACTED]		√
Spectral Domain Optical Coherence Tomography (SD-OCT) Images obtained by certified examiner (technician acceptable). Reading of images done by central reading center. Refer to Central Reading manual for instructions.	[REDACTED]	√	√
[REDACTED]	[REDACTED]	√	
Dilated Fundus Examination (peripheral retina, macula, choroid, optic nerve, retinal/detachment, retinal or vitreous hemorrhage, vitreous hemorrhage density, vitreous cells.)	[REDACTED]	√	

Assessment	Time points	Primary Endpoints/ Safety	Efficacy Endpoints of Clinical Relevance
Microperimetry Automated microperimetry to be performed in Cohort 3 (optional) and in Cohort 4. Must be conducted by certified examiner (technician is acceptable). Reading of images done by central reading center. Refer to Central Reading manual for instructions.		√	√
Fluorescein Angiography (FA) Standard procedure for detection of CNV . Must be conducted by certified examiner (technician is acceptable): at [REDACTED] to verify dry AMD and absence of neovascular (wet) AMD , and on final exam at end of study; optional FA during follow-up in cases of suspected conversion to wet AMD		√	
Intraocular Pressure (IOP) One IOP measurement per eye		√	
Slit Lamp Examination (Lids/Lashes, Conjunctiva, Cornea, Iris, Aqueous Cells, Aqueous Flare and Lens) Must be conducted by certified examiner (technician is acceptable)		√	
Physical Examination including ECG, Vital Signs Clinical evaluation by the study-dedicated investigator or designee will be performed at several time points to evaluate pre- and post-implantation subject condition including immunosuppression treatment safety (see below)**		√	
Malignancy Assessment In the case of any suspected malignancies at screening, subject should be referred to appropriate medical specialist.		√	
Complete Blood count (including differential) / Chemistry (including Serum Electrolytes) / Coagulation / Urinalysis		√	
Serology Assessment including testing for HIV, CMV, EBV , HBV and HCV		√	
[REDACTED]		√	
Immunology		√	

Assessment	Time points	Primary Endpoints/ Safety	Efficacy Endpoints of Clinical Relevance
HLA-typing will be performed during [REDACTED] or during one of the subsequent visits if not performed during [REDACTED]			
[REDACTED]	[REDACTED]	√	
QuantIFERON (state of inoculation) To detect tuberculosis (TB) disease	[REDACTED]	√	
[REDACTED]	[REDACTED]	√	
Fundus Autofluorescence Imaging (FAF) Images obtained by certified examiner (technician acceptable). Reading of images done by central reading center. Images are done by using blue light Heidelberg instrumentation. Each assessment for each subject must be done with the same camera used at Screening. Refer to Central Reading manual for instructions.	[REDACTED]	√	√
Color Fundus Photography (CFP) Images obtained by certified examiner (technician acceptable). Reading of images done by central reading center. Color Images are done by using Zeiss instrumentation. Each assessment for each subject must be done with the same camera used at Screening. Refer to Central Reading manual for instructions.	[REDACTED]	√	√
Reading Speed Test This test is mandatory for subjects are proficient in English.	[REDACTED]		√
NEI VFQ-25 Quality of Life (examiner version) 25 item subject reported outcome. Scores range from 0-100 with the higher score indicating better visual function.	[REDACTED]		√

Assessment	Time points	Primary Endpoints/ Safety	Efficacy Endpoints of Clinical Relevance

Functional Reading Independence (FRI) Index            The FRI index is a patient-reported outcome measure developed specifically for use in GA subjects. Scores derived from the index range from 1 (unable to do) to 4 (total independence) and may be analyzed as either categorical (which is preferred from a regulatory perspective) or continuous variables.            This test should be administered in the subject’s mother tongue language and is not applicable for Cohorts 1-3
			√

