
Functional Reading Independence (FRI) Index The FRI index is a patient-reported outcome measure developed specifically for use in GA subjects. Scores derived from the index range from 1 (unable to do) to 4 (total independence) and may be analyzed as either categorical (which is preferred from a regulatory perspective) or continuous variables. This test should be administered in the subject's mother tongue language and is not applicable for Cohorts 1-3
	
[REDACTED]
		
√

The schedule of assessments for screening and first year during the study are detailed in [Table 2](#). The schedule of assessments for long-term follow-up is detailed in [Section 15](#).

Visit #	
Day (or M=month=28)	
General (continued)	
General safety assessment (AEs and concomitant medication)	
Surgery of OpRegen® implantation	
Investigators global evaluation of device performance	
Intraoperative Video/OCT Imaging	
Discharge from the hospital ¹⁵	
Functional Testing	
BCVA	
Low Luminance BCVA ¹⁶	
SD- OCT (central reading)	
Fundus Autofluorescence (FAF) (central reading)	
Color Fundus Photography (CFP) (central reading)	
Microperimetry ¹⁷ (central reading)	
Fluorescein Angiography (FA) (central reading)	

¹³ The eye chosen for OpRegen implantation will be the eye with worse visual function.

¹⁴ Investigators global evaluation will be determined pre- and post-implantation for participants in cohort 4 who receive subretinal cell delivery of OpRegen via [REDACTED]

¹⁵ Hospitalization is not applicable for U.S subjects.

¹⁶ Performance of Low Luminance BCVA is dependent on subject's BCVA. This test is optional for cohort 4 subjects with low vision who are not able to perform this test and is not applicable for cohorts 1-3.

¹⁷ Microperimetry for cohort 3 [optional], but is required for all [REDACTED] subjects and all cohort 4 US-treated subjects

At screening, a full ocular history will be obtained and an ophthalmic examination including the following assessments will be performed, as detailed in [Table 2](#):

- Demographics
- Inclusion/Exclusion Criteria
- BCVA
- Low Luminance BCVA (optional)
- SD-OCT (central reading)
- Microperimetry (central reading) cohort 3 [optional], but is required for all [REDACTED] subjects and all cohort 4 US-treated subjects and Cohort 4)
- Fluorescein Angiography (FA) (central reading)
- Fundus Autofluorescence (FAF) (central reading)
- Color Fundus Photography (CFP) (central reading)
- Dilated Fundus Examination
- IOP
- Slit Lamp Exam

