 - Low Luminance BCVA (optional for cohort 4 subjects with low vision who are not able to perform this test and is not applicable for cohorts 1-3)
 - SD-OCT (central reading)
 - FAF (central reading)
 - CFP (central reading) – optional, as per investigator discretion.
 - CBC (including differential)
 - Chemistry (including Serum Electrolytes)
 - Coagulation
 - Urinalysis
 - Rheumatology (including ESR and CRP)
 - HLA typing if not done previously

- [REDACTED]
- General safety assessments (AEs and concomitant medications)
 - Vital signs
 - Dilated Fundus Examination
 - IOP
 - Slit Lamp Exam
 - Immunosuppression assessment
- [REDACTED]
- BCVA
 - Low Luminance BCVA (optional for cohort 4 subjects with low vision who are not able to perform this test and is not applicable for cohorts 1-3)
 - SD-OCT (central reading)
 - FAF (central reading)
 - CFP (central reading)
 - Microperimetry (central reading) cohort 3 [optional], but is required for all [REDACTED] subjects and all cohort 4 US-treated subjects
 - CBC (including differential)
 - Chemistry (including Serum Electrolytes)
 - Coagulation
 - Urinalysis
 - Rheumatology (including ESR and CRP)
 - HLA typing if not done previously

- [REDACTED]
- [REDACTED]
- [REDACTED]
- General safety assessments (AEs and concomitant medications)
 - Vital signs
 - Dilated Fundus Examination
 - IOP
 - Slit Lamp Exam
 - Immunosuppression assessment
 - BCVA
 - Low Luminance BCVA (optional for cohort 4 subjects with low vision who are not able to perform this test and is not applicable for cohorts 1-3)
 - SD-OCT (central reading)
 - FAF (central reading)
 - CFP (central reading) – optional, as per investigator discretion

- [REDACTED]
- General safety assessments (AEs and concomitant medications)
 - Vital signs
 - Physical examination
 - Dilated Fundus Examination
 - IOP
 - Slit Lamp Exam
 - Immunosuppression assessment
 - BCVA
 - Low Luminance BCVA (optional for cohort 4 subjects with low vision who are not able to perform this test and is not applicable for cohorts 1-3)
 - Microperimetry (central reading) cohort 3 [optional], but is required for all [REDACTED] subjects and all cohort 4 US-treated subjects
 - SD-OCT (central reading)
 - FAF (central reading)
 - CFP (central reading)
 - [REDACTED]
 - CBC (including differential)
 - Chemistry (including Serum Electrolytes)
 - Coagulation
 - Urinalysis
 - Rheumatology (including ESR and CRP)
 - Malignant hematological transformation
 - HLA typing if not done previously

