#### 4.1.2 Baseline and Change from Baseline

Unless indicated otherwise, change from baseline (CFB) will be calculated as follows, where the baseline assessment is the last assessment before OpRegen injection:

$$\text{CFB} = \text{Value at Visit} - \text{Baseline}$$

Percent change from baseline (PCFB) will be calculated as follow:

$$\text{PCFB (\%)} = 100 * (\text{Value at Visit} - \text{Baseline}) / \text{Baseline}$$

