## 6.3 Procedures for Handling Missing Data and Outliers

Missing or incomplete dates will be imputed per [Section 4.1.1](#) for the purposes of determining treatment emergence. All other missing data will not be imputed, unless otherwise noted.

All unscheduled visit data will be included in data listings. In the data summary tables, the presence of missing data will be indicated by the inclusion of a 'missing' category with categorical data, and a count and percentage of missing observations for continuous numeric data, where applicable.

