### 7.1.10 Efficacy Analyses

All efficacy data will be listed for all subjects. Efficacy summaries will be presented for the Intent to Treat Population for all variables.

- Directional change in the geographic atrophy ([GA](#)) lesion area over time
- Overall change in the [GA](#) lesion area of the study eye over time using [FAF](#)
- Change from baseline over time in [BCVA](#) as measured by Early Treatment Diabetic Retinopathy Study ([ETDRS](#)) chart
- Change from baseline over time in Low Luminance [BCVA](#)
- Change from baseline over time in [IOP](#)

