### **Statistical summary conventions**

For tables, sample sizes for each treatment group will be presented as totals in the column header (N=x), where appropriate. Sample sizes shown with summary statistics are the number (n) of subjects with non-missing values.

Summaries for categorical variables will include only categories that subjects had a response in. Percentages corresponding to null categories (cells) will be suppressed. All summaries for continuous variables will include: N, mean, and SD. Other summaries (e.g. median, quartiles, 5%, 95% intervals, CV or %CV) will be used as appropriate. All percentages should be rounded and reported to a single decimal place (xx.x%). If percentages are reported as integers, percentages greater than 0% but <1% will be reported as <1%, whereas percentages greater than 99% but <100% will be reported as >99%. A percentage of 100% will be reported as 100%. No value of 0% should be reported. Any computation of percent that results in 0% is to be reported as a blank. P-values will be reported with three decimal places with a leading zero (0.001). P-values <0.001 will be reported as <0.001.

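### Eyes that become too poorly sighted for the low-luminance BCVA test can drop out of its mean change, which then tends to understate worsening by an amount the documents do not let us fix

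*SAP*

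**What the plan says.** SAP Table 1 describes the test: a 2.0-log-unit neutral density filter is placed before the study eye and an ETDRS chart is read. It adds: "This test is optional as subjects with low vision will not be able to perform this test and is not applicable for Cohorts 1-3". Only Cohort 4, with 12 eyes, can therefore contribute.

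The protocol ties performance of the test to current acuity. Footnote 16 to Table 2 states: "Performance of Low Luminance BCVA is dependent on subject's BCVA". The opt-out is not limited to screening. Post-implantation visit lists, including the end-of-study visit, describe the test as "optional for cohort 4 subjects with low vision who are not able to perform this test".

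The analysis rules are in the SAP:

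- Section 7.1.10 lists "Change from baseline over time in Low Luminance" BCVA among the efficacy analyses.
- Section 4.1.2 defines change as the visit value minus baseline, "where the baseline assessment is the last assessment before OpRegen injection".
- Section 6.3 covers missing values other than dates: "All other missing data will not be imputed, unless otherwise noted". No exception is noted for LL-BCVA. Tables are to carry "a count and percentage of missing observations for continuous numeric data, where applicable".
- Section 10.0 adds: "Sample sizes shown with summary statistics are the number (n) of subjects with non-missing values".

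Protocol 22.6 has a different rule: last observed value, where appropriate.

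Neither document gives a score for an eye that cannot do the test, asks why a test was not done, or plans a sensitivity analysis.

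**The concern.** Whether an LL-BCVA value exists depends on the quantity being measured. If a Cohort 4 eye reads letters through the filter at baseline and is later skipped because it sees too poorly, its outcome is at or near the worst possible. Under the written rules that outcome becomes a blank, and the mean change is taken over the eyes that can still do the test.

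With at most 12 eyes, one or two such losses can shift the mean. The protocol describes the disease as progressive, and SAP section 9.0 plans an analysis at Year 5, so some losses are plausible. At stake is a descriptive efficacy result that looks more stable than the eyes were, and that may be used in designing later studies (protocol 6.2).

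**Working it through.** **Inputs from the documents.** Cohort sizes are 3 + 3 + 6 + 12 = 24, which agrees with the stated total; LL-BCVA applies to the last 12. Standard BCVA at entry to Cohort 4 is 29 to 64 letters. The documents give no LL-BCVA baseline, standard deviation, expected change or expected number of untestable eyes, so there is no plan figure to reproduce. All letter values below are assumptions.

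**Fixed scenarios.** Let *k* of 12 eyes lose the test from a baseline of *b* letters, while each other eye changes by -2.

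- Observed-only mean (SAP rules): -2.0 for every *k*.
- Mean with inability scored as 0 letters: [(12 - k)(-2) - k·b] / 12.
- Gap: k(b - 2) / 12.

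| Baseline *b* of lost eyes | k = 1: 0-scored mean (gap) | k = 2 | k = 3 |
|---|---|---|---|
| 5 | -2.25 (0.25) | -2.50 (0.50) | -2.75 (0.75) |
| 10 | -2.67 (0.67) | -3.33 (1.33) | -4.00 (2.00) |
| 20 | -3.50 (1.50) | -5.00 (3.00) | -6.50 (4.50) |

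For example, with k = 2 and b = 10: (10 × (-2) - 20) / 12 = -40/12 = -3.33, and the gap is 2 × 8 / 12 = 1.33. The gap is positive only when *b* exceeds 2, that is, when the lost eyes fell by more than the others.

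**Floor model.** The scenarios fix *b* by hand, but eyes near the floor are the likeliest to become untestable. A simulation of 100,000 trials of 12 eyes took baseline LL-BCVA as normal with SD 12 and change as normal with SD 8. An eye was untestable when its score was below 1 letter. Average gaps in letters:

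| Baseline mean | Mean change -3 | Mean change -6 | Mean change -10 |
|---|---|---|---|
| 15 | 0.73 | 0.77 | 0.54 |
| 25 | 0.34 | 0.41 | 0.42 |
| 35 | 0.11 | 0.15 | 0.22 |

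At baseline mean 15 and mean change -3, for instance, the observed-only mean is -1.59 against -2.32 with inability scored 0. Every gap is toward less worsening. The average number of eyes lost runs from 0.16 to 3.22.

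**Protocol 22.6 as a remedy.** If the last observed value of each lost eye is its baseline, that eye contributes a change of 0. With the others at -2, the mean is (12 - k)(-2)/12: -1.83, -1.67 and -1.50 for k = 1, 2 and 3. That lies further from the 0-scored result than the observed-only mean does.

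**The case against.** A reader might infer that worsening is hidden. The documents do not support that. The *n* shown with each summary would fall, section 6.3 provides missing counts where applicable, and sections 7.0 and 7.1.10 promise listings of all efficacy data. Standard BCVA in the same eyes is a separate endpoint with its own table. What stands against this is narrower: no reason for a missing test is required, so inability cannot be told from an omitted optional test, and section 11.0 names no LL-BCVA table, figure or listing.

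A second objection is that a missing value is not inevitable. SAP Table 1 scores standard BCVA as the count of letters correctly read, so an attempted test with nothing read could be recorded as 0. Footnote 16 could also be read as meaning subjects who can never do the test and so have no baseline. This is fair, but the opt-out recurs at follow-up visits, and a test skipped there has no value.

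Third, the exclusion also works the other way. An eye unable at baseline that later reads letters has no change score, so its gain is lost too. That stands, and the fix must show both counts.

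A reader might also infer a bias of several letters that grows with follow-up. The larger figures need eyes falling from about 20 letters to none while the others barely change. In the floor model at baseline mean 15, the gap goes 0.73, 0.77, 0.54 as mean decline steepens, so steady growth is not shown.

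Finally, this is one of ten efficacy endpoints in a study without power calculation or formal testing. That limits its weight but does not correct the summary.

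**Conclusion.** The point holds in a limited form. The rules as written let a Cohort 4 eye with a baseline LL-BCVA leave the mean change when it is skipped for poor vision. The mean is then biased toward less worsening if such eyes declined more than the rest. The protocol's last-observed-value rule does not repair this.

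The size cannot be established from the documents. With 12 eyes, 1 to 3 lost and the others at -2, it runs from 0.25 to 4.5 letters depending on where the lost eyes started; the floor model averages 0.1 to 0.8. Both rest on assumed letter scores and on counting inability as 0. The net direction, once eyes unable at baseline are considered, is not established either. The matter deserves correction because the remedy is cheap, but it affects one exploratory summary and no decision rule.

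**What to change.** In SAP 6.3 and 7.1.10, for eyes with a baseline LL-BCVA:

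- Score a visit as 0 letters where source or CRF shows that the test was attempted with nothing read, or was not done because vision was too low. Leave values missing for any other reason.
- Show the observed-only mean beside the 0-scored mean.
- Report, per visit, the number of eyes that became unable and the number unable at baseline that could later be tested.
- Where the reason was not recorded, say so and show the 0-scored result only as a sensitivity bound.
- State that this replaces the last-observed-value rule of protocol 22.6 for this endpoint.

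The cost is SAP wording and some source review for at most 12 subjects. Neither document shows that the reason for a test not done was captured. The SAP describes implantation in the past tense, so some reasons may not be recoverable, and assigning them in an open-label study involves judgement. The reported change is likely to look slightly less favourable.
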